7.2. Adverse Events of Special Interest Analyses

- Adverse events of special interest (AESIs) reported by the investigator as systemic reactions (further categorised by the investigator as either allergic [type I hypersensitivity] or other systemic reactions and assessed against Sampson criteria for anaphylaxis) are collected via targeted eCRF within the study. Local injection site reactions are also collected via targeted eCRF within the study.
- AESIs of opportunistic infections, malignancies, serious cardiac vascular and thromboembolic (CVT) events and serious ischemic events will be identified from a list of relevant preferred terms maintained within a project level reference dataset created based on the MedDRA dictionary available at the time of database freeze for this study. Further details of how relevant preferred terms are identified are given in the Program Safety Analysis Plan (PSAP).
- Separate summary tables showing the number and percent of participants with each type of AESI, broken down by preferred term will be created.
- For each type of AESI a profile summary table will be produced containing information including, but not be limited to, the number of occurrences of the event, event characteristics, time to onset, intensity, outcome and action taken.
- Separate listings of AESIs identified by the investigator as anaphylaxis, allergic (type I hypersensitivity), other systemic reactions and local injection site reactions will be

produced, as well as listings of opportunistic infections, malignancies, serious CVT events and serious ischemic events.

7.3. Clinical Laboratory Analyses

Laboratory evaluations including the analyses of Chemistry laboratory tests, Hematology laboratory tests, Urinalysis, and liver function tests will be based on GSK Core Data Standards. The details of the planned displays are in [Appendix 8: List of Data Displays](#).

7.4. Other Safety Analyses

The analyses of non-laboratory safety test results including ECGs and vital signs will be based on GSK Core Data Standards, unless otherwise specified. The details of the planned displays are presented in [Appendix 8: List of Data Displays](#).

8. IMMUNOGENICITY ANALYSES

The immunogenicity analyses will be based on the Safety population, unless otherwise specified.

8.1. Overview of Immunogenicity Analyses

For the immunogenicity assessment, two types of anti-drug antibody (ADA) assays will be performed, a binding anti-drug antibody assay and a neutralizing antibody assay.

For the binding assay, there will be a three tiered analysis: screening, confirmation and titration. The screening assay produces a result of positive or negative relative to a screening cut point. Positive samples continue with the confirmation assay, which also produces a result of positive or negative relative to a confirmation cut point. For positive confirmation samples, a titre value will also be obtained to quantify the degree of binding in a titration assay and the sample will be tested with the neutralizing assay, which also reports results as positive or negative.

The binding ADA assay results at each visit will be summarised negative or positive. In addition, the highest post-baseline binding ADA assay confirmatory result obtained for a subject will be summarised. Subjects with both positive and negative results will be identified in the positive category. Summary statistics for the titre result by visit will also be presented.

A summary of adverse events by highest post-baseline binding ADA assay confirmatory result (as defined above) will be produced.

A summary of treatment emergent positive confirmatory binding ADA assay results in the subset of subjects who did not have a positive confirmatory binding ADA assay result prior to the dosing of study treatment will also be presented.

Neutralizing antibody assay results will be summarised by visit. In addition, the highest post-baseline neutralising antibody assay result during the treatment period of the study will be summarised, with subjects with both positive and negative results identified in the positive category.

Immunogenicity data will be listed for subjects with at least one positive screening binding assay result.

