5. STUDY DESIGN

5.1. Overall Design

Figure 1 Study schematic

This is a multi-centre, open-label extension, 20-week treatment period, safety study of mepolizumab in adolescent and adult participants with HES who took part in the phase 3 Study 200622 (Figure 1).

Study 200622 participants who meet one of the following criteria will be screened to continue with Study 205203:

- i. Completion of the 32-week treatment period in Study 200622,
- or*
- ii. If the participant was withdrawn from study treatment prematurely during the 200622 study, but continued in the study per protocol (including HES flare-related assessments) until 32 weeks from randomization.

Eligible participants will receive 300mg SC mepolizumab every 4 weeks starting approximately 32 weeks after the first dose of study treatment in Study 200622. In this OLE Study 205203, the final dose of mepolizumab will be administered at Visit 5 (Week 16). Assessments during the Visit 6 (20 weeks after first dose and 4 weeks after the last dose) will complete the study treatment period.

During Study 205203, investigators will be blinded to the blood eosinophil count (Section 12.2) for the sample collected at Visit 1 (1st dosing visit), after which blood eosinophil counts will be unblinded starting at Visit 2. Investigators may adjust the participants' background HES therapy per standard of care starting at Visit 2 (approximately 4 weeks after the first dose).

Participants who complete assessments at Visit 6 (Week 20) may continue with mepolizumab treatment via mepolizumab HES expanded access (e.g., MHE104317, MHE112562), where local regulation permits. Study 205203 participants who do not continue with mepolizumab HES expanded access will have an additional follow-up assessment at Visit 7 (28 weeks after first dose and 12 weeks after the last dose of mepolizumab).

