13. APPENDICES

13.1. Appendix 1: Schedule of Activities

13.1.1. Protocol Defined Schedule of Events

Procedure Study Visit	Screening/Baseline 1	20-Week Treatment Period					WD (4 weeks post-last dose) ± 1 wk	Study Visit 7 Additional follow-up (12 weeks post-last dose ± 1 wk)	Flare	Notes
		2	3	4	5	6				
Study Weeks	0	4 ± 1 wk	8 ± 1 wk	12 ± 1 wk	16 ± 1 wk	20 ± 1 wk				
Informed consent	X									
Inclusion and exclusion criteria	X									
Demography	X									
Full physical examination including height and weight	X									
Past and current medical conditions	X									
Urine pregnancy test (WOCBP only) – serum test if locally required	X	X	X	X	X	X	X	X		Test is required for WOCBP on study treatment until the last follow-up.
Clinical safety laboratory assessments (include liver chemistries)	1	2	2	2	2	1	1		2	1: Hematology, chemistry, aldolase, troponin, urinalysis 2: Hematology, chemistry, aldolase, troponin
PK	X					X	X	X		
Immunogenicity (Anti-drug antibody)	X					X	X	X		
12-lead ECG	X					X	X			

Procedure	Screening/Baseline	20-Week Treatment Period					WD (4 weeks post-last dose) ± 1 wk	Study Visit 7 Additional follow-up (12 weeks post-last dose ± 1 wk)	Flare	Notes
		2	3	4	5	6				
Study Visit	1									
Study Weeks	0	4 ± 1 wk	8 ± 1 wk	12 ± 1 wk	16 ± 1 wk	20 ± 1 wk				
Vital signs	X	X	X	X	X	X	X		X	
HES Core Assessments/HES flare details	X	X	X	X	X	X	X		X	
Study treatment	X	X	X	X	X					
AE review	X	X	X	X	X	X	X	X	X	
SAE review	X	X	X	X	X	X	X	X	X	
Concomitant medication review	X	X	X	X	X	X	X	X	X	

wk: week

- The baseline visit is the exit visit (32 weeks after randomization) for Study 200622. Assessments that are captured as part of the exit visit for Study 200622 do not have to be repeated. Information will be transferred accordingly.
- Biological sample collection (for clinical safety laboratory, PK, and immunogenicity) is done prior to administration of study treatment on dosing visits (Visits 1 2, 3, 4, 5) as specified in the SoA.
- WD: Prematurely discontinuation of mepolizumab (~4 weeks after the last dose of mepolizumab).
- Visit 7 - Additional follow-up is required 12 weeks after the last dose of mepolizumab for participants who do not continue with mepolizumab via MHE104317/MHE112562 at that time.

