2.51.	Safety	LIVER1	Summary of Liver Monitoring/Stopping Event Reporting		SAC
2.52.	Safety	LIVER10	Summary of Hepatobiliary Laboratory Abnormalities		SAC
ECG					
2.53.	Safety	EG1	Summary of ECG Findings by Visit	Include worst case post-baseline. If there are unscheduled assessments add footnote: "Note: Worst case post baseline Includes scheduled and unscheduled assessments."	SAC
2.54.	Safety	EG2	Summary of Change from Baseline in ECG Values by Visit	Include baseline values	SAC
2.55.	Safety	EG10	Summary of Maximum QTc Values Post-Baseline Relative to Baseline by Category	QTc(B) and QTc(F) If there are unscheduled assessments add footnote: "Note: Includes scheduled and unscheduled assessments."	SAC

No.	Population	IDSL / Example Shell	Title	Programming Notes	Deliverable
2.56.	Safety	EG11	Summary of Maximum Increase in QTc Values Post-Baseline Relative to Baseline by Category	QTc(B) and QTc(F) If there are unscheduled assessments add footnote: "Note: Includes scheduled and unscheduled assessments."	SAC
Vital Signs					
2.57.	Safety	VS1	Summary of Vital Signs by Visit		SAC
2.58.	Safety	VS1	Summary of Change from Baseline in Vital Signs by Visit	Include baseline values	SAC
Immunogenicity					
2.59.	Safety	SAFE_T3	Summary of Binding Antibody by Visit	Include highest post baseline result.	SAC
2.60.	Safety	SAFE_T3	Summary of Binding Antibody By Visit – Subjects Without Positive Result Prior to Dosing	Post-Week 0 visits only, plus highest post baseline result.	SAC
2.61.	Safety	SAFE_T4	Summary of Neutralising Antibody by Visit	Include highest post baseline result.	SAC

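### SAP 8.1 stops the highest neutralising-antibody result at the end of the treatment period but puts no such limit on binding ADA, so a completer's Visit 7 sample counts for one and not the other.

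*SAP*

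**What the plan says.** SAP 8.1 plans a highest-result summary for each of the two assays. For binding ADA, "the highest post-baseline binding ADA assay confirmatory result obtained for a subject will be summarised". For neutralising antibody, "the highest post-baseline neutralising antibody assay result during the treatment period of the study will be summarised". The same section plans by-visit summaries for both assays, without a period limit. When a binding sample is confirmed positive, "the sample will be tested with the neutralizing assay"; no visit is excepted.

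The schedule (protocol Section 2, SAP 13.1.1) takes immunogenicity samples at Visit 1, Visit 6, the WD visit and Visit 7. Protocol 5.1 places the last dose at Visit 5 (Week 16) and says: "Assessments during the Visit 6 (20 weeks after first dose and 4 weeks after the last dose) will complete the study treatment period". Visit 7 is 12 weeks after the last dose and is only for participants who do not continue in expanded access.

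In SAP 13.8.5, Table 2.59 (binding, by visit) and Table 2.61 ("Summary of Neutralising Antibody by Visit") have the same programming note. It asks for the highest post-baseline result and names no period. Protocol 10.3.1 plans a count of participants with antibodies over the study. SAP 2.4, which lists changes from the protocol's analysis plan, does not mention a treatment-period limit.

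**The concern.** Only confirmed binding positives reach the neutralising assay, so the neutralising summary describes a subset of the binding positives. A reader will set the two highest-result rows side by side and assume that they cover the same samples. Under the wording of 8.1 they do not, no reason is given, and the display list does not repeat the restriction. A programmer who follows 8.1 and one who follows the note to Table 2.61 could produce different rows from the same data.

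ADA is one of the two primary endpoints. The sample left out is the last one taken, and it is one of only two scheduled post-baseline samples for a completer who does not enter expanded access. What is at stake is whether the neutralising row can miss a positive that the binding row has counted.

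**Working it through.** No sample size or error rate is involved. The check is schedule arithmetic and a comparison of texts.

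**Reproducing the plan's timing.** Last dose Week 16 + 4 weeks = Week 20 (Visit 6). Last dose Week 16 + 12 weeks = Week 28 (Visit 7). Both agree with protocol 5.1.

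**Could visit windows bring a completer's Visit 7 into the treatment period?** With ±1 week windows:
- latest Visit 6: 20 + 1 = Week 21
- earliest Visit 7: last dose at 16 − 1 = Week 15, plus 12 − 1 = 11 weeks, gives Week 26
- Visit 7 in days after the last dose: 11 × 7 = 77 to 13 × 7 = 91

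Visit 7 therefore falls after the end of the 20-week period. It also falls after last dose + 28 days, the rule that SAP 13.2.1 uses for on-treatment adverse events. A completer's Visit 7 sample is excluded on either reading.

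**Early discontinuers.** The 12-week sample falls at:

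| Last dose | 12-week sample | Within 20 weeks? | Within last dose + 28 days? |
|---|---|---|---|
| Week 0 | Week 12 | yes | no |
| Week 4 | Week 16 | yes | no |
| Week 8 | Week 20 | yes | no |
| Week 12 | Week 24 | no | no |

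For the first three rows the answer depends on what 'treatment period' means, and the SAP does not say.

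**Visit 6 and WD under a 28-day reading.** Visit 6 can fall 19 − 17 = 2 to 21 − 15 = 6 weeks after the last dose, that is 14 to 42 days. The WD visit can fall 3 to 5 weeks after it, that is 21 to 35 days. A strict 28-day reading would also drop some samples taken within their visit windows.

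**Following a completer with a neutralising-positive sample at Visit 7 and none before.** The sample must first be confirmed positive for binding.
- Highest binding result: positive, because Visit 7 is post-baseline.
- Highest neutralising result under 8.1: not positive. If Visit 6 was binding-positive but neutralising-negative, the row shows negative. If Visit 7 is the first binding positive, there is no post-baseline neutralising result within the period, and the SAP does not say whether that appears as negative or as missing.
- Highest neutralising result under the Table 2.61 note: positive.

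A narrower window can remove participants from the count of neutralising positives but cannot add any.

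**The case against.** The strongest reply is that little depends on this row. No data are lost: Visit 7 neutralising results appear in the by-visit summary, and Listing 32 covers everyone with a positive screening binding result. The protocol's stated analysis is the count of participants with antibodies, and the binding summary already includes Visit 7. All of this stands, and it limits the point to one supplementary row.

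It can also be said that a table note is shorthand and need not repeat every qualifier. The mock shell is not in the documents, so it may carry the limit. That is fair: text and display list are unaligned, and more than that cannot be shown. Nor does the order of the assays dictate a reporting window; the SAP uses on-treatment windows elsewhere, for example for blood eosinophils (11.1.4). But it gives no reason for using different windows for the two assays here.

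A reader might infer more than the documents support:
- *That the neutralising share of ADA positives is understated.* No such share is planned and no denominator is given. If a participant first positive at Visit 7 is shown as missing, that person leaves both numerator and denominator. If the sample is neutralising-negative, no positive is lost. The direction of any effect on a share is not known.
- *That the share shifts by 14 to 20 percentage points.* This takes the protocol's 6% ADA incidence (100 mg SC, severe asthma) times 80 to 120 participants, giving 4.8 to 7.2 positives, and moves one of them (1/7 = 14%, 1/5 = 20%). The dose and disease differ, 80 to 120 is the size of the parent study and so an upper bound here, and nothing shows that even one participant would move.
- *That most completers have only the Visit 6 sample.* The documents give no figure for continuation into expanded access. If most do continue, few attend Visit 7 and the problem shrinks.
- *That the 12-week sample is always excluded.* For a last dose at Week 8 or earlier it may fall within the 20-week period.

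**Conclusion.** The mismatch holds on the wording of SAP 8.1. The highest binding result uses all post-baseline samples; the highest neutralising result stops at the end of a treatment period that is not defined for immunogenicity. For completers this excludes Visit 7, and it does not match the note to Table 2.61 or protocol 10.3.1. The highest-neutralising row could miss a positive.

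The size cannot be computed from the documents. The affected group is narrow: participants with a Visit 7 sample that is neutralising-positive and with no earlier post-baseline neutralising positive. The number is probably small and may be zero. The conclusion assumes that the neutralising assay is run on Visit 7 samples as 8.1 describes, and that 8.1 rather than the table note governs the programming. This is a minor correction and does not threaten the primary safety analysis.

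**What to change.** In SAP 8.1, delete the qualifier that limits the highest neutralising result to the treatment period. Both highest-result summaries then use all post-baseline samples, including WD and Visit 7, in line with Table 2.61 and protocol 10.3.1.

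If an on-treatment summary is also wanted, define its window, apply it to both assays and label it as such in the tables. Last dose + 28 days is one candidate, but it would need an allowance for Visit 6 and WD samples taken later within their visit windows. A labelled on-treatment version would also suit Table 2.9, which sets on-treatment adverse events against a binding category that a Visit 7 sample may determine; deleting the qualifier leaves that table unchanged.

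The cost is one phrase, with no new data and no new assays.

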9. EFFICACY ANALYSES

9.1. Exploratory Efficacy Analyses

9.1.1. Rate of HES Flares

9.1.1.1. Endpoint / Variables

Definition of HES Flare

A HES flare is defined as an HES-related clinical manifestation based on a physician-documented change in clinical signs or symptoms (worsening symptoms and/or elevated blood eosinophil level) resulting in the need for either of the following:

- An increase from the most recent dose in the maintenance OCS dose (prednisone/prednisolone equivalent) by at least 10mg/day for 5 days
- An increase in or addition of any cytotoxic and/or immunosuppressive HES therapy from/to the most recent dose of HES therapy.

To be considered as an HES flare, the most recent dose of HES therapy must not have changed for at least 4 weeks. This ensures that failed reductions in HES therapy are not misclassified as an HES flare.

The definition of HES flare for this study (205203) is different from that for the preceding, randomized Study 200622. This difference in definitions is due to the requirement during Study 200622 to avoid decreases in background HES therapy that may confound a blinded subject's clinical status as well as the requirement during Study 200622 to blind blood eosinophil levels. In Study 205203, all participants will receive mepolizumab and investigators will be unblinded to blood eosinophil levels starting 4 weeks after the first dose (Visit 2) so that they may adjust background HES therapy as per standard of care (SoC).

Derivation of Endpoint

The rate of HES flares will be calculated for each subject as the number of observed HES flares divided by the time (expressed in years) between the first dose of study treatment in Study 205203 and either the Week 20 visit date if available, or otherwise the study withdrawal date (see Section [13.4.4](#)).

The rate of HES flares will also be calculated separately using data from Study 200622 only, for those subjects continuing into Study 205203.

The number of observed HES flares will be calculated for each subject as the number of unique starting dates for HES flares. To be considered as a separate episode of HES flare, the onset date of an HES flare must be at least 14 days apart from the resolution date of the preceding HES flare.

9.1.1.2. Summary Measure

The rate/year of HES flares.

9.1.1.3. Strategy for Intercurrent (Post-Randomization) Events

The treatment effect to be estimated (estimand) will be the ‘treatment policy’ effect of initial randomised treatment. A treatment policy strategy will be used for the intercurrent events of discontinuation of study medication. For subjects withdrawing prematurely from the study during the 20-week treatment period, all data up to the time of study withdrawal will be used to calculate the rate of HES flares.

9.1.1.4. Statistical Analyses / Methods

Endpoint
Rate of HES flares.
Model Specification

 Analysis using a negative binomial generalised linear model with a log-link function, including terms for baseline OCS dose from study 200622 (continuous scale), region and observed time (as an offset variable). The model estimated mean flare rate per year will be weighted according to the observed proportion of the categorical covariates in the study data by inclusion of the OM (obsmargins) option in the LSMEANS statement of the GENMOD procedure. A separate model will be fitted to data from Study 200622 for those subjects continuing into Study 205203.
Model Checking & Diagnostics

 The fit of the negative binomial generalised linear model will be investigated by calculating and plotting standardised deviance residuals.
Model Results Presentation

 Median rate/year on raw data values for Study 200622 (Week 0 – Week 32, double-blind) and Study 205203 (Week 32 – Week 52, open-label). Adjusted mean rate/year from negative binomial model and 95% confidence interval for Study 200622 (Week 0 – Week 32, double-blind) and Study 205203 (Week 32 – Week 52, open-label).
Subgroup Analyses

 No subgroup analyses will be performed on this endpoint.
Sensitivity and Supportive Statistical Analyses

 No sensitivity analyses will be performed

9.1.2. Change in mean daily OCS dose from Weeks 0-4 to Weeks 16-20

9.1.2.1. Endpoint / Variables

The mean daily OCS (prednisone or equivalent) dose for each 4 week period (Week 0-4, Week 4-8, Week 8-12, Week 12-16 and Week 16-20) for each subject will be calculated as the sum of the daily doses of OCS during each period divided by the total number of days, 28. For each subject, the prednisone equivalent daily dose for each day will be determined as described in Section 13.4.4.

Subjects withdrawing from the study prematurely will have mean daily OCS (prednisone or equivalent) dose calculated using available data up to study withdrawal date only (divided by the number of days for which there is available data).

The change in the mean daily OCS dose from Week 0-4 to Week 16-20 will be calculated for each subject as the mean daily OCS dose for Week 16-20 minus the mean daily OCS dose for Week 0-4. The change in the mean daily OCS dose from Week 0-4 to each 4-week period (Week 4-8, Week 8-12 and Week 12-16) will be calculated using the same formula. The change in mean daily OCS dose will be summarised separately for a) all subjects and b) for subjects with a mean Week 0-4 OCS dose > 0mg.

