4. OBJECTIVES AND ENDPOINTS

[figure not shown]
Objectives	Endpoints

Primary - Safety
 
 To describe the long-term safety profile of mepolizumab in participants with HES who took part in Study 200622. 	
 Adverse events (AEs) [serious and non-serious] Anti-drug antibody

Other – Safety
 
 To describe the long-term safety profile of mepolizumab in participants with HES who took part in Study 200622. 	
 Vital signs 12-lead ECG Hematological and clinical laboratory tests

Exploratory - Efficacy
 
 To assess the effect of long-term use of mepolizumab on multiple clinical outcomes. 	
 Rate of HES flare[#] Change in the mean daily OCS dose from Weeks 0-4 to Weeks 16-20 Proportion of participants who achieve a mean daily OCS (prednisone/prednisolone or equivalent) dose of ≤ 7.5mg during Weeks 16-20

Pharmacodynamic (PD)
 
 To assess the effect of long-term use of mepolizumab on a PD marker 	
 Blood eosinophil levels

[#] HES flare as defined in Section 9.1.1.

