2.4. Changes to the Protocol Defined Statistical Analysis Plan

- More detail was added to the protocol defined endpoint, change in mean daily OCS dose from Weeks 0-4 to Weeks 16-20. This additionally includes the change in mean daily OCS dose from Weeks 0-4 to Weeks 4-8, Weeks 8-12 and Weeks 12-16.
- An additional endpoint of the proportion of patients who achieve a mean daily OCS (prednisone/prednisolone or equivalent) dose reduction of 50% or more from Week 0-4 to Week 16-20 will be reported, for those subjects with a mean OCS dose during Week 0-4 greater than 0mg.

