9.1.4.1. Endpoint / Variables

Subjects who achieve a mean daily OCS (prednisone/prednisolone or equivalent) reduction of 50% or more throughout each four-week period (Week 4-8, Week 8-12, Week 12-16 and Week 16-20) will be identified from the concomitant medications results, as defined in Section 13.4.4. This endpoint will be summarised for subjects with a mean Week 0-4 OCS dose > 0mg only.

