13.4. Appendix 4: Derived and Transformed Data

13.4.1. General

Multiple Measurements at One Analysis Time Point

 • May arise when unscheduled visits are re-assigned to a nominal visit (see Section 13.1.1). If there is data at the nominal visit, the nominal visit data will be used in the summary tables and figures. All assessments will be listed. • Participants having both High and Low values for Normal Ranges at any post-baseline visit for safety parameters will be counted in both the High and Low categories of “Any visit post-baseline” row of related summary tables. This will also be applicable to relevant Potential Clinical Importance summary tables. • If multiple ECG assessments are performed at a single time point, for each ECG parameter, the mean of the parameter values from replicate ECGs will be used in the derivation of any summary statistics for that ECG parameter. All data will be listed.
Study Day

 • Calculated as the number of days from the date of the first dose of open-label mepolizumab: 
 • Ref Date = Missing → Study Day = Missing • Ref Date < First date of open-label mepolizumab → Study Day = Ref Date – First date of open-label mepolizumab • Ref Date ≥ First date of open-label mepolizumab → Study Day = Ref Date – (First date of open-label mepolizumab) + 1

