The definition of HES flare for this study (205203) is different from that for the preceding, randomized Study 200622. This difference in definitions is due to the requirement during Study 200622 to avoid decreases in background HES therapy that may confound a blinded subject’s clinical status as well as the requirement in Study 200622 to blind blood eosinophil levels. In Study 205203, all participants will receive mepolizumab and investigators will be unblinded to blood eosinophil levels starting 4 weeks after the first dose (Visit 2) so that they may adjust background HES therapy as per SoC.

Rate of HES Flares

- For subjects completing the study, the rate of HES flares will be calculated as

$$\frac{365.25 \times \text{Number of observed HES flares}}{\text{Date of Week 20 (Visit 6)} - \text{Date of first dose of mepolizumab} + 1}$$
- For subjects withdrawing prematurely from the study, the rate of HES flares will be calculated as

$$\frac{365.25 \times \text{Number of observed HES flares}}{\text{Date of study withdrawal} - \text{Date of first dose of mepolizumab} + 1}$$

The number of HES flares is the number of unique starting dates for HES flares. To be considered as a separate episode of HES flare, the start date of an HES flare must be at least 14 days apart from the resolution date of the preceding HES flare.

Oral Prednisone Equivalent Daily Dose

- For each subject, oral prednisone equivalent daily dose (mg) on each day of the study will be identified from the concomitant medications page
- Partial start and end dates for concomitant medications will be handled as described in Section 13.5.2.
- Corticosteroids will be identified from the list of coded concomitant medications for the study, by merging with the GSK respiratory medication class (RMC) reference data set by component code. This reference data is created by dictionary specialists who identify a list of component terms for corticosteroids, which then undergo clinical review to ensure the correct classification is assigned.
- Only corticosteroids recorded with route = “PO” will be considered as oral corticosteroids.
- Subjects not receiving OCS therapy on any day of the study will be assigned a prednisone equivalent daily dose of 0 mg for that day.
- The corticosteroid conversion factors in the table below will be used to scale each corticosteroid dose to a prednisone equivalent dose.

Medication Name	Scaling Factor
Betamethasone	8.33
Budesonide ¹	0
Cortisone	0.2

Dexamethasone	6.67

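### The added ≥50% OCS reduction endpoint can count the end of a temporary steroid course in Weeks 0-4 as steroid sparing

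*SAP*

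**What the plan says.** - **Protocol endpoint.** Protocol Section 4 lists, as an exploratory endpoint, "Change in the mean daily OCS dose from Weeks 0-4 to Weeks 16-20". Weeks 0-4 is thus the protocol's own reference for the change in mg. SAP 9.1.2.1 carries it out as the "mean daily OCS dose for Week 16-20 minus the mean daily OCS dose for Week 0-4".
- **Endpoint added by the SAP.** SAP 2.4 states that the proportion with a "dose reduction of 50% or more from Week 0-4 to Week 16-20 will be reported". It limits this to participants whose mean over the reference period is above zero, and SAP 9.1.4.1 repeats the restriction: "This endpoint will be summarised for subjects with a mean Week 0-4 OCS dose > 0mg only". The result goes into Table 3.8. The same subset defines Table 3.6, the mg change among OCS users.
- **How the mean is built.** Each period mean is the sum of daily doses "divided by the total number of days, 28". Under SAP 13.4.4, for each participant, the "oral prednisone equivalent daily dose (mg) on each day of the study will be identified from the concomitant medications page". All corticosteroids with oral route count (budesonide has a factor of 0). No rule separates maintenance from temporary courses.
- **Where Week 0 lies.** The Schedule of Activities places the first open-label dose at Week 0, and SAP 13.4.1 defines study day the same way: "Calculated as the number of days from the date of the first dose of open-label mepolizumab". The reference period is therefore on treatment.
- **Flares and adjustment.** Under Protocol 9.1.1, flares are recorded from Visit 1, the smallest OCS flare increase is 10 mg/day for 5 days, and investigators are encouraged to return to the pre-flare regimen. Under Protocol 5.1, background therapy may be adjusted from Visit 2, scheduled at Week 4 ± 1 week.

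**The concern.** A ≥50% responder table is read as evidence that maintenance steroid was spared. The SAP's rule cannot tell a lower maintenance dose from the end of a temporary course. A short oral course in Weeks 0-4 raises the reference, or creates one where there was none. The return to the previous dose, which the protocol encourages after a flare, then registers as a reduction. For participants with no maintenance OCS it also changes the denominator, because the course itself admits them to the subset.

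Table 3.8 is shown by previous treatment as well as overall, and its subset is smaller than the Safety population, so a few such participants could visibly move a percentage. No sensitivity analysis is described for the OCS endpoints.

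**Working it through.** The documents give no response rate or sample size for this endpoint, so there is no planned figure to reproduce. The check applies the SAP's own arithmetic.

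**Inputs from the documents:** 28-day denominator (SAP 9.1.2.1); smallest OCS flare increase, 10 mg/day × 5 days = 50 mg-days (Protocol 9.1.1); Visit 2 at Week 4 ± 1 week, so at most about 7 of the 28 reference days can follow an adjustment made at that visit.
**Assumed:** maintenance dose M, any larger course (E mg/day extra for d days), and the timing of a taper.

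**1. No maintenance OCS (M = 0).** The Week 0-4 mean is E×d/28, which is above 0 for any course, so the participant enters the subset. At 0 mg in Weeks 16-20 the reduction is 100% whatever the course size. For the smallest flare increase the mean is 50/28 = 1.79 mg. For a single 5 mg tablet on one day (assumed) it is 5/28 = 0.18 mg. Both score 100%.

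**2. On maintenance, temporary course, then return to M.**

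Reference = M + E×d/28; later dose = M; scored reduction = (E×d/28) / (M + E×d/28). This is ≥50% exactly when M ≤ E×d/28. The true change in maintenance is zero throughout.

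| Course in Weeks 0-4 | E×d/28 = largest M scored as a responder |
|---|---|
| 10 mg × 5 days (documented minimum) | 1.79 mg/day |
| 10 mg × 14 days (assumed) | 5.0 mg/day |
| 30 mg × 10 days (assumed) | 10.7 mg/day |
| 30 mg × 14 days (assumed) | 15.0 mg/day |

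With the documented minimum, M = 1 scores 1.79/2.79 = 64.1%, a responder. M = 2.5, 5 and 10 score 41.7%, 26.3% and 15.2%, not responders. With 30 mg × 14 days on M = 10, the reference is 25 mg and the score is 15/25 = 60%.

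**3. Taper begun at an early Visit 2.** A single step of fraction r, taken t days before Day 28 and then held, gives reference M(1 − r×t/28). A true r of at least 50% is missed only if r < 0.5/(1 − 0.5×t/28).

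- t = 7: 0.5/0.875 = 57.1%. A cut from 10 to 5 mg has reference 8.75 mg and scores 3.75/8.75 = 42.9%.
- t = 3: 52.8%.
- t = 1: 50.9%.

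Withdrawal to 0 mg always scores 100%.

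**4. Effect on a table column.** The documents do not give the subset size; assume 15 to 30 per column. One participant already in the subset who is wrongly scored a responder moves the percentage by 100/30 = 3.3 to 100/15 = 6.7 points. One participant added as in step 1 moves it by at most 100/(n + 1), that is 100/31 = 3.2 to 100/16 = 6.3 points.

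**The case against.** The reference has a rationale. Weeks 0-4 is the protocol's own OCS reference, and because background therapy may be adjusted only from Visit 2, it is largely a pre-taper window. The SAP declares the added endpoint openly, and one reference for all OCS summaries is a defensible choice. This stands as a reason to leave the mg-change endpoint alone. It does not address temporary escalations inside the window, and both the responder threshold and the above-0-mg subset are SAP additions.

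The only documented course size is the flare minimum, which misclassifies only participants on 1.79 mg/day or less; anything larger is assumed. This also stands, and it limits what can be said for participants on ordinary maintenance doses. It does not limit the 0 mg case, where any course suffices.

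Other displays limit the harm. Mean dose in each period (Table 3.4), change in all participants (Table 3.5) and the proportion at or below 7.5 mg (Table 3.7) do not depend on the subset. Listings 9 and 11 allow affected participants to be traced. Table 3.8 itself would still not show the artefact.

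Replacing the reference outright with a maintenance-only dose would not compare like with like, since the Week 16-20 mean counts every oral corticosteroid. Changing the subset everywhere would also alter Table 3.6. Both points stand, and the fix below avoids them.

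**Conclusion.** The point holds for temporary courses. Under the stated rule, a participant with no maintenance OCS and any oral course in Weeks 0-4 is scored a 100% reducer once the course is over. A participant on maintenance is misclassified only if the excess averaged over 28 days is at least the maintenance dose: 1.79 mg/day for the documented minimum, and 5 to 15 mg/day for the assumed 14-day courses.

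Three stronger readings are tempting but not supported.

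- **That early tapering hides many true responders.** Within the Visit 2 rule, only one-step cuts of 50% to about 57% are missed, and only when the visit is a full week early. The error understates steroid sparing, so it is conservative. Safety reductions or protocol deviations could widen it, but the documents give no frequency.
- **That the distortion differs between the previous-placebo and previous-mepolizumab columns.** The documents give no frequency of early courses in either group.
- **That the Week 0-4 reference departs from the protocol.** It is the protocol's own reference for the mg change.

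The endpoint is exploratory, the analysis is descriptive and no test is planned, so no formal conclusion depends on it. The change is an optional improvement.

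**What to change.** Keep the protocol's Week 0-4 mg-change endpoint and Tables 3.5 and 3.6 as specified. In SAP 2.4, 9.1.4 and Table 3.8:

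1. Define the subset as participants whose prednisone-equivalent OCS dose, derived by the Section 13.4.4 rules, is above 0 mg on the day before the first open-label dose. This removes the 0 mg case, unless a course is already running on that day.
2. Keep the Week 0-4 comparison as the main row and add a supportive row scoring ≥50% reduction against that pre-dose daily dose. For example, M = 5 with 30 mg extra for 10 days scores 68.2% in the main row and 0% in the supportive row. A cut from 10 to 5 mg at Day 21 scores 42.9% and 50%.
3. Footnote the number of participants with a temporary course running at Visit 1 or started in Weeks 0-4. Protocol 7.6 already requires reason for use, dates and dose.
4. Write the percentage formula into Section 13.4.4. SAP 9.1.4.1 refers there for it, but that section defines only the mean and its change. Say how a Week 0-4 mean of 0 mg in a pre-dose user is scored, since the percentage is then undefined.

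**Cost:** some programming and a second reference in one exploratory table, with no new data collection. **Remaining weakness:** a single pre-dose day is set against a 28-day mean, and a course already running at Visit 1 still inflates the pre-dose reference. This can happen, because Protocol 5.4 allows therapy to be increased for worsening in Study 200622. The footnote count shows how often it does.
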